4.2.5.2 Derivations and Censoring Rules

Patients who have not progressed or died at the time of analysis will be censored at their last evaluable MRI assessment. However, if the patient progresses or dies after two or more consecutive missed MRI assessments, the patient will be censored at the time of the latest evaluable MRI assessment prior to the missed visits. The details of censoring rules are listed in Table 12.

The derivation formula for PFS is date of PFS event or censoring – date of randomisation + 1.

If the patient has no evaluable MRI assessments post-baseline, they will be censored at Day 1 unless they die within two cycles from baseline. The PFS time will be derived based on actual MRI assessment dates and not visit dates.

Table 12: Summary of Censoring Guidelines for PFS

Assessment	Date of event, death or censoring	PFS outcome
Death, PD	MRI assessment of earliest sign of PD or death date if the event is death	Event
No PD or death at time of analysis or lost to follow-up	Latest evaluable MRI assessment	Censored
Death or PD after ≥ 2 missed assessments	Latest evaluable MRI assessment prior to the two missed assessments	Censored
No evaluable MRI assessment or no baseline data and no death within two cycles from baseline	Day 1	Censored

MRI, magnetic resonance imaging; PD, progressive disease; PFS, progression-free survival.

Based on the scheduled visit assessment scheme (i.e., every 4 cycles until Cycle 24 and every 6 cycles from then onwards), the definition of 2 missed visits will change over time and is calculated as the protocolled time between 2 subsequent scans + the protocol-allowed visit window for an early visit at the previous assessment + the protocol-allowed visit window for a late visit at the expected assessment:

Table 13: Two Missed Visits Window Rule

Scheduled assessments	Previous REiNS assessment	Two missed visits window
Q16w ± 1 week up to Week 80	Up to Week 15 (<Day 105)	33 weeks (231 days)
	Week 15 – Week 79 ≥105 - <553	34 weeks (238 days)
	Week 79 – Week 95 ≥ 553 - <665	42 weeks (294 days)
Q24w ± 1 week	Week 95 ≥665	50 weeks (350 days)

REiNS, Response Evaluation in Neurofibromatosis and Schwannomatosis.

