4.2.1 Primary Endpoint

4.2.1.1 PN Volumes and Derivation of REiNS Tumour Response

For all patients, the REiNS tumour data will be used to determine each patient's visit response according to the REiNS criteria. Tumour assessments will be measured by volumetric MRI.

Baseline radiological tumour assessments will be performed during the 28-day screening period. Unless clinically indicated otherwise, tumour assessments of the target and non-target PN (if relevant) will be obtained at screening and every 4 cycles (16 ± 1 weeks) relative to the date of the first dose for the first 24 cycles. From the end of Cycle 24, tumour assessments will be performed every 6 cycles (24 ± 1 week) as long as the patient remains on study intervention.

Volumetric MRI assessment will be performed by AstraZeneca's appointed imaging contract research organisation (CRO) according to the REiNS criteria. A double read of all MRI scans will be performed. The ICR reviewers will be blinded to the study intervention group. Further details of the ICR will be documented in the independent review charter (IRC).

All volumetric MRI scans for all patients (including those at unscheduled visits or outside visit windows) will be collected on an ongoing basis and sent to an AstraZeneca-appointed imaging CRO for central analysis. The investigator will select the target PN and non-target PN (if relevant) based on the results of the screening PN assessments. Details about target PN location and non-target PN location (if relevant) will also be collected and sent to the imaging CRO to ensure that the independent reviewer also follows the most clinically relevant PN. The imaging CRO will determine the tumour measurements of the target PN and non-target PN.

If an unscheduled assessment is performed (e.g., to investigate clinical signs/symptoms of progression) and the patient has not progressed, the subsequent assessments at the next scheduled visit must be performed. This schedule is to be followed in order to minimise any unintentional bias caused by some patients being assessed at a different frequency than other patients.

To determine the level of response, the TL and NTL volume will be assessed as the average PN volumes from the double read, and follow-up scans will be compared to the baseline scan or the scan at the time of best response after documenting a CR/PR for the same PN.

If the interim analysis takes place, then:

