4.6.1 Exposure

4.6.1.1 Definitions and Derivations

Exposure will be defined as follows:

- Total (or intended) exposure = min (last dose date of selumetinib/placebo where dose > 0 mg, date of death, DCO Date) – first dose date of selumetinib/placebo + 1
- Actual exposure = Total (or intended) exposure – total duration of dose interruptions, where total (or intended) exposure will be calculated as above. A dose interruption is defined as either any day with dose = 0 mg, or any half day where planned frequency is bid but actual frequency is daily, during the treatment period.

This calculation will use the individual start and stop dates on the EX form of the CRF, which will account for any dose interruptions. The actual exposure calculation makes no adjustment for any dose reductions that may have occurred.

Exposure will also be measured by the number of cycles received. A cycle corresponds to a period of 28 days. A cycle will be counted if study intervention is started even if the full dose is not delivered.

Exposure will be derived for selumetinib and placebo. Patients who only received selumetinib will only have exposure records for selumetinib, while patients who received placebo and selumetinib will have exposure records for selumetinib and placebo.

Patients Who Permanently Discontinue During a Dose Interruption

If a patient permanently discontinues study intervention during a dose interruption, then the date of last administration of study medication will be used in the calculation of exposure. In this case, the interruption would not be included in the summary tables, but it will be included in the listings.

Relative Dose Intensity

Relative dose intensity (RDI) is the percentage of the actual dose delivered relative to the intended dose through to study intervention discontinuation. RDI will be defined as follows:

RDI = $100\% * \frac{d}{D}$, where d is the actual cumulative dose delivered up to the actual last day of dosing and D is the intended cumulative dose up to the day of treatment discontinuation or the actual last day of dosing. D is the total dose that would be delivered if the patient received the planned dose as per the CRF. Intended cumulative dose will be calculated by summing the individual doses that should have been received up to and including the last day of treatment according to the protocol planned dose and schedule. This is given by:

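### The PFS Day-1 censoring rule turns a death on Days 57 to 231 with no evaluable scan into zero follow-up, in conflict with the scan schedule and with the missed-assessment rule in the same SAP section

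*SAP*

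**What the plan says.** SAP 4.2.5.1 defines PFS as time from randomisation to progression by central review or to death, whatever the cause. SAP 4.2.5.2 then gives two rules that bear on an early death.

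- **Day-1 rule.** Patients without an evaluable post-baseline MRI are censored at Day 1 "unless they die within two cycles from baseline". The last row of Table 12 assigns Day 1, censored, to "No evaluable MRI assessment or no baseline data and no death within two cycles from baseline".
- **Missed-assessment rule.** Table 12 censors "Death or PD after ≥ 2 missed assessments" at the last evaluable scan before the gap. With fewer missed assessments, a death is an event. Table 13 turns two missed assessments into days; its first row, for a previous assessment before Day 105, gives 33 weeks, or 231 days.

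Two definitions elsewhere in the SAP fix the time scale. SAP 4.6.1.1 states: "A cycle corresponds to a period of 28 days". SAP 4.2.1.1 schedules MRI "every 4 cycles (16 ± 1 weeks) relative to the date of the first dose for the first 24 cycles".

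Protocol 9.4.2.3.3 describes censoring only for participants who have neither progressed nor died, and leaves the detailed rules to the SAP.

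**The concern.** The two-cycle exception expires seven weeks before the first scan window opens (Day 56 against Day 105). A patient who dies on Day 50 is a PFS event. A patient who dies on Day 80 has also missed no scan, yet is censored at time zero. Nothing in the visit schedule makes Day 56 a meaningful boundary, and the other rule in the same section would treat the Day 80 death as an event.

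What is at stake is the Kaplan-Meier PFS curve in the Selumetinib FAS, in particular the Month 4 and Month 8 estimates, which are the first two that SAP 4.2.5.4 reports. Deaths that meet the endpoint definition would not count, and those patients would leave the risk set at the start. The supplementary analysis in SAP 4.2.5.5 lifts only the missed-assessment rule, so it does not restore them.

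**Working it through.** **Inputs.** Cycle length 28 days (SAP 4.6.1.1). Scans every 16 ± 1 weeks from first dose up to Cycle 24, then every 24 ± 1 weeks (SAP 4.2.1.1). Table 13 windows (SAP 4.2.5.2). Planned arm size 73 (SAP 3.4). Days are counted from first dose, as a working assumption, because the rule does not date its baseline.

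**1. Reproduce Table 13.** Window = two scan intervals + early-visit allowance + late-visit allowance.

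| Previous assessment | Weeks | Days | Table 13 |
|---|---|---|---|
| Before Day 105 | 16 + 16 + 0 + 1 = 33 | 231 | agrees |
| Day 105 to before Day 553 | 16 + 16 + 1 + 1 = 34 | 238 | agrees |
| Day 553 to before Day 665 | 16 + 24 + 1 + 1 = 42 | 294 | agrees |
| Day 665 onward | 24 + 24 + 1 + 1 = 50 | 350 | agrees |

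The first row reproduces only with a zero early-visit allowance. That fits a patient whose last assessment is baseline, which is the patient the Day-1 rule addresses.

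**2. Length of the exception.** 2 × 28 = 56 days.

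**3. First scan.** 4 × 28 = Day 112; window (16 − 1) × 7 = Day 105 to (16 + 1) × 7 = Day 119.

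**4. Compare the rules for a death with no evaluable scan.**

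| Day of death | Scheduled assessments missed | Day-1 rule | Missed-assessment rule |
|---|---|---|---|
| 1 to 56 | 0 | event | event |
| 57 to 119 | 0 | censored at Day 1 | event |
| 120 to 231 | at most 1 | censored at Day 1 | event |
| After 231 | 2 or more | censored at Day 1 | censored at last evaluable scan (baseline) |

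The rules disagree over 231 − 56 = 175 days: 119 − 56 = 63 days with no scan missed, and 231 − 119 = 112 days with at most one missed. That is 175/231 = 76% of the Table 13 window.

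**5. Effect on the curve.** Take n = 73 and no other events or censoring, with d such deaths. As written, the estimate stays at 100% with 73 − d at risk. If the deaths count, it is (73 − d)/73 once they have occurred. The documents give no expected d; 1 to 5 is an assumed range for illustration.

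| d | As written | Deaths counted | Difference (points) |
|---|---|---|---|
| 1 | 100% | 98.6% | 1.4 |
| 2 | 100% | 97.3% | 2.7 |
| 3 | 100% | 95.9% | 4.1 |
| 5 | 100% | 93.2% | 6.8 |

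**6. Direction.** From the day of the uncounted death onward, the curve as written lies above the correct one. Before that day, losing the patient from the risk set can lower the curve slightly if another event came first. With one earlier event, it is 71/72 = 98.61% instead of 72/73 = 98.63%, which is negligible.

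**The case against.** **The Day-1 rule may be a deliberate, specific rule.** It addresses patients with no post-baseline scan, and the SAP never says outright that such patients fall under the missed-assessment row. The first row of Table 13 could also cover an early unscheduled scan. This is a fair reading, although the zero early-visit allowance points to baseline. It does not rescue the rule: even as an override, it censors at time zero patients who have missed no scheduled scan.

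**Cycles may be a slip for assessments.** SAP 4.2.6.2 refers back to 4.2.5.2 for the derivation of missed cycles, when that section derives missed assessments. If the same slip occurred here, the intended exception already matches Table 13 and no event is lost. That is plausible and supports the proposed correction. But the SAP defines a cycle as 28 days, and a programmer following the text would use 56 days.

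**The impact is close to nil.** Plexiform neurofibromas are benign tumours and entry requires ECOG 0 or 1, so early deaths should be rare. Deaths are also reported in the adverse event tables and listings. This stands, and it sets the level of the point.

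**Stronger readings that the documents do not support.** A reader might infer that the rule removes the earliest deaths. It does not: Days 1 to 56 remain events. A reader might also infer that every death after two cycles without a scan is wrongly lost. After Day 231 two assessments have been missed, and the general rule would censor the patient at baseline anyway. Nor does the 1.4 points per death estimate an actual bias; it is conditional on such a death occurring.

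**Conclusion.** The rule is wrong as written, over a bounded span. A death on Days 57 to 231 with no evaluable post-baseline scan is censored at time zero, against the PFS definition, the scan schedule and the section's own missed-assessment rule. The clearest part is Days 57 to 119, where no scan can have been missed. For Days 120 to 231 the conflict rests on reading the first row of Table 13 as applying to patients whose last assessment is baseline, which its arithmetic supports.

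Each affected death is worth about 1.4 points on the Kaplan-Meier estimate, assuming 73 patients and no other events or censoring. The count is not given and is probably very small. Single-arm PFS is a descriptive secondary endpoint outside the multiple testing procedure, so no confirmatory conclusion depends on it. TTP does not count deaths, and DOR includes only responders, who have scans, so neither is affected. This is a minor wording correction.

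**What to change.** In the text of SAP 4.2.5.2 and in the last row of Table 12, replace the two-cycle limit with *within two scheduled MRI assessments (33 weeks, 231 days, per Table 13)*.

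Two further statements are needed for the correction to be complete:

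- **Anchor date.** Name the date from which the window runs, for example randomisation, where the PFS clock starts. The baseline scan may fall anywhere in the 28-day screening period and study days run from first dose, so the present reference to baseline has no fixed date.
- **SAP 4.2.16.** Say whether the Day-1 rule applies to PFS during the randomised period. That section takes its definition from 4.2.5 and waives only the two-missed-visit rule. If the Day-1 rule carries over, it could also affect the trigger of at least 5 events that decides whether the analysis is done.

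The cost is SAP wording and the matching line in the derivation program. No new data or analyses are required.

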4.2.5.3 Intercurrent Events

The approach for intercurrent events mostly follows the same as outlined for the primary endpoint in Section 4.2.1.7. However, the first intercurrent event for the primary endpoint, as detailed in Table 8, will change to be ‘Post randomised study intervention discontinuation due to any reason’ since early crossover from placebo is not relevant to the analysis of PFS, as analysis is performed on patients randomised to selumetinib (see Section 4.2.5.4). And any post randomised study intervention discontinuation should not be restricted to prior to Cycle 16, as PFS is evaluated over the whole while on-treatment MRI volumetric assessments period (Section 3.3.2.1).

4.2.5.4 Primary Analysis of PFS

A KM plot of PFS will be presented including a patients-at-risk table. The percentage of PFS at Months 4, 8, 12, 16, 20, and 24 and every 6 months thereafter will be summarised based on the KM method. If more than 50% of patients progress in either arm, the median PFS and 95% CIs will also be calculated using the KM method and presented in the summary table.

Data are summarised and analysed using the Selumetinib FAS. Data are included as outlined in Sections 4.2.5.1 and 4.2.5.2, adhering to the intercurrent event strategy (refer to Section 4.2.5.3).

4.2.5.5 Supplementary Analyses of PFS

The following supplementary analyses will be performed:

- PFS will be calculated based on all on-treatment MRI volumetric assessments without excluding scans during study intervention interruption. The analysis will follow the same methods as the primary analysis of PFS.
- If there is at least one patient who progresses or dies after two or more consecutive missed MRI assessments, then the same PFS analysis will be done without this specific censoring rule (i.e., also including progression or death results after two or more consecutive missed MRI assessments). PFS will be derived using the while on-treatment MRI volumetric assessments (see Section 3.3.2.1).
- A supplementary analysis will be performed including all randomised patients who received at least one dose of selumetinib (Extended Selumetinib FAS). In this analysis, the baseline MRI scan for patients randomised to placebo will be defined as the last MRI scan performed on placebo intervention prior to starting on selumetinib intervention. PFS will be derived using the while on-treatment MRI volumetric assessments (see Section 3.3.2.1).
- Individual subject-level PFS (months) will be summarised in a time-to-event listing for DCO2 and DCO3 for the Extended Selumetinib FAS.

4.2.6 Time to Progression

4.2.6.1 Definition

Time to progression (TTP) will be defined as the time from the date of randomisation until the date of the first documented objective disease progression by ICR per REiNS criteria. Objective disease progression is defined as PD as per overall visit response. TTP will be derived using the while on-treatment MRI volumetric assessments (see Section 3.3.2.1).

4.2.6.2 Derivations and Censoring Rules

Patients who have not progressed at the time of analysis will be censored at their last evaluable MRI assessment. However, if the patient progresses after two or more missed assessments, the patient will be censored at the latest evaluable MRI assessment prior to the two missed assessments.

The derivation formula for TTP is date of progression or censoring – date of randomisation + 1.

If the patient has no evaluable MRI assessments post-baseline, they will be censored at Day 1. The TTP will always be derived based on actual MRI assessment dates and not visit dates.

Refer to Section [4.2.5.2](#) for further details on the derivation of two or more missed cycles.

4.2.6.3 Intercurrent Events

The approach for intercurrent events mostly follows the same as outlined for the primary endpoint in Section [4.2.1.7](#). However, the first intercurrent event for the primary endpoint, as detailed in [Table 8](#), will change to be ‘Post randomised study intervention discontinuation due to any reason’ since early crossover from placebo is not relevant to the analysis of TTP, as analysis is performed on patients randomised to selumetinib (see Section [4.2.6.4](#)). And any post randomised study intervention discontinuation should not be restricted to prior to Cycle 16, as TTP is evaluated over the whole while on-treatment MRI volumetric assessments period (Section [3.3.2.1](#)).

4.2.6.4 Primary Analysis of TTP

A KM plot of TTP will be presented including a patients-at-risk table. The percentage TTP at Months 4, 8, 12, 16, 20, and 24 and every 6 months thereafter will be summarised based on the KM method. If more than 50% of patients progress in either arm, the median TTP and 95% CIs will also be calculated using the KM method and presented in the summary table.

Data are summarised and analysed using the Selumetinib FAS. Data are included as outlined in Sections [4.2.6.1](#) and [4.2.6.2](#), adhering to the intercurrent event strategy (refer to Section [4.2.6.3](#)).

4.2.6.5 Supplementary Analyses of TTP

- TTP will be calculated based on all on-treatment MRI volumetric assessments without excluding scans during study intervention interruption. The analysis will follow the same methods as the primary analysis of TTP.
- If there is at least one patient who progresses or dies after two or more consecutive missed MRI assessments, then the same TTP analysis will be done without this specific censoring rule (i.e., also including progression results after two or more consecutive missed MRI assessments). TTP will be derived using the while on-treatment MRI volumetric assessments (see Section [3.3.2.1](#)).
- A supplementary analysis will be performed including all randomised patients who received at least one dose of selumetinib (Extended Selumetinib FAS). In this analysis, the baseline MRI scan for patients randomised to placebo will be defined as the last MRI scan performed on placebo intervention prior to starting on selumetinib intervention. TTP will be derived using the while on-treatment MRI volumetric assessments (see Section [3.3.2.1](#)).
- Individual subject-level TTP (months) will be summarised in a time-to-event listing for DCO2 and DCO3 for the Extended Selumetinib FAS.

4.2.7 Time to Response

4.2.7.1 Definition

Time to response (TTR) will be defined as the time from the date of randomisation until the date of the first documented objective response (which is subsequently confirmed; cCR or cPR) as determined by ICR per REiNS criteria (i.e., date of first response – date of randomisation + 1). TTR will be derived using the while on-treatment MRI volumetric assessments (see Section 3.3.2.1). The date of first documented response should coincide with that used for the DOR endpoint (see Section 4.2.4).

4.2.7.2 Derivations and Censoring Rules

The TTR will always be derived based on the actual MRI assessment dates and not visit dates.

Only patients in the Selumetinib FAS who have achieved a cCR or a cPR prior to selumetinib discontinuation will be evaluated for TTR.

The derivation formula for TTR is date of first documentation of cCR or cPR – date of randomisation + 1.

4.2.7.3 Intercurrent events

The approach for intercurrent events mostly follows the same as outlined for the primary endpoint in Section 4.2.1.7. However, the first intercurrent event for the primary endpoint, as detailed in Table 8, will change to be ‘Post randomised study intervention discontinuation due to any reason’ since early crossover from placebo is not relevant to the analysis of TTR, as analysis is performed on patients randomised to selumetinib (see Section 4.2.7.4). And any post randomised study intervention discontinuation should not be restricted to prior to Cycle 16, as TTR is evaluated over the whole while on-treatment MRI volumetric assessments period (Section 3.3.2.1).

4.2.7.4 Primary Analysis of Time to Response

A KM plot of TTR will be presented including a Patients-at-Risk table. The percentage TTR at months 4, 8, 12, 16, 20 and 24, and every 6 months thereafter will be summarised based on the KM method. Median TTR and 95% CIs will also be calculated using the KM method and presented in the summary table.

Data is summarised and analysed using the Selumetinib FAS. Data is included as outlined in Section 4.2.7.1 adhering to the intercurrent event strategy (refer to Section 4.2.7.3).

4.2.7.5 Supplementary Analyses of TTR

- TTR will be calculated based on all on-treatment MRI volumetric assessments without excluding scans during study intervention interruption. The analysis will follow the same methods as for the primary analysis of TTR.

- A supplementary analysis will be performed including all patients in the Extended Selumetinib FAS with a cCR or cPR prior to selumetinib discontinuation. In this analysis, the baseline MRI scan for patients randomised to placebo will be defined as the last MRI scan performed on placebo intervention prior to starting on selumetinib intervention. TTR will be derived using the while on-treatment MRI volumetric assessments (see Section 3.3.2.1).
- Individual subject-level TTR (months) will be summarised in a time-to-event listing for DCO2 and DCO3 for the Extended Selumetinib FAS.

4.2.8 Best Percentage Change From Baseline in Target PN Volume During the Randomised Period

